2.1.4.2 Deaths

The deaths' observation periods are per the observation periods defined above.

- On-study: deaths occurring during the on-study observation period (PAP and ETP respectively),
- On-treatment: deaths occurring during the on-treatment epoch (PAP and ETP respectively),
- Post-treatment: deaths occurring during the post treatment epoch (PAP and ETP respectively).

2.1.4.3 Laboratory safety variables

Clinical laboratory data consist of blood analysis, including hematology, clinical chemistry, and urinalysis. Clinical laboratory values after conversion will be analyzed into standard international units and international units will be used in all listings and tables.

Blood samples for clinical laboratories will be taken as specified in the study protocol. The laboratory parameters will be classified as follows:

- Hematology: red blood cell count, hematocrit, hemoglobin, white blood cell count with differential count (neutrophils, eosinophils, basophils, monocytes, and lymphocytes), platelets,
- Biochemistry:
 - Plasma/serum electrolytes: sodium, potassium, chloride, calcium,
 - Liver function: aspartate aminotransferase (AST), alanine aminotransferase (ALT), alkaline phosphatase, gamma-glutamyl transferase, total and conjugated bilirubin,
 - Renal function: creatinine, blood urea nitrogen, uric acid,
 - Metabolic panel: glucose, albumin, total proteins, total cholesterol, triglycerides,
 - Potential muscle toxicity: creatine kinase, creatine kinase with MB fraction, lactate dehydrogenase.

Urinalysis will include urine color, appearance, specific gravity, proteins, glucose, erythrocytes, leukocytes, ketone bodies, and pH to be assessed:

- Qualitatively: A dipstick is to be performed on a freshly voided specimen for qualitative detection using a reagent strip.
- Quantitatively: A quantitative measurement for protein, erythrocytes, and leukocytes count will be required in the event that the urine sample test is positive for any of the above parameters by urine dipstick (eg, to confirm any positive dipstick parameter by a quantitative measurement).

2.1.4.4 Vital signs variables

Vital signs include heart rate, systolic and diastolic blood pressure, respiratory rate, temperature, and oxygen saturation.

2.1.4.5 Electrocardiogram variables

Standard 12-lead ECGs will be recorded after at least 15 minutes in the supine position using an electrocardiographic device. The following will be assessed: heart rate, rhythm, interval from start of the Q wave to the end of the S wave (QRS), interval between the peaks of successive QRS complexes (RR), interval from the beginning of the P wave until the beginning of the QRS complex (PR), interval between the start of the Q wave and the end of the T wave (QT), QT interval corrected for heart rate (QTc) automatic correction evaluation (by the ECG device), QRS axis, left ventricular hypertrophy criteria, right ventricular hypertrophy criteria, repolarization charges, and overall cardiac impression for each patient. For Day 1 only, and prior to receiving IMP, 3 ECGs within 5 minutes will be performed with at least 1 minute between 2 replicates.

2.1.4.6 Physical examination

Physical examination parameters include assessments of the patient's general appearance; skin; head, eyes, ears, nose, and throat; examinations of lymph nodes, abdomen, extremities/joints, neurological and mental status; heart and respiratory auscultation; peripheral arterial pulse; and pupil, knee, Achilles, and plantar reflexes. Head circumference and Tanner stage of sexual maturation will be assessed as part of the physical examination in pediatric patients at baseline and yearly thereafter.

2.1.4.7 Body weight and height

Body weight will be measured in kilograms and collected in the e-CRFs monthly for pediatric patients and every 3 months throughout the duration of the study for adults. More frequent weight may be obtained at the discretion of the investigator.

Standing height will be measured in all patients at baseline and annually thereafter, and in pediatric patients additionally every 3 months up to Week 73 and then every 6 months. If possible, height will be measured in the morning of the study visit day, prior to the pulmonary function testing, and by using the same stadiometer for all measurements.

2.1.4.8 Immunogenicity

Patients in the avalglucosidase alfa treatment arm will be tested for anti-avalglucosidase alfa antibodies and patients in the alglucosidase alfa treatment arm will be tested for anti-alglucosidase alfa antibodies in PAP (up to Week 49). Cross reactivity will be assessed at Week 25 and Week 49 during the PAP. Patients who are positive for anti-avalglucosidase alfa antibodies will be tested to determine if the antibodies cross-react with alglucosidase alfa and patients who are positive for anti- alglucosidase alfa antibodies will be tested to determine if the antibodies cross-react with avalglucosidase alfa at these timepoints. In the open label follow-up phase and beyond, patients from each treatment arm will be tested for anti-avalglucosidase alfa antibodies.

Samples will be collected from patients for evaluation of ADAs every month during the blinded treatment period and for the first 6 months of the open-label avalglucosidase alfa long term follow-up phase, and then every 3 months throughout the duration of the study. In addition, samples will be collected from all randomized patients at Week 2 (Day 8) and Week 52 (1 week after the first ETP treatment) to monitor for an early antibody response. ADA seropositive patient serum will be assessed for neutralizing antibodies to avalglucosidase alfa and/or alglucosidase alfa, as appropriate, including inhibition of enzyme activity and uptake.

The qualitative sample status of the ADA will be assessed and be categorized into the following classes:

- ADA-negative sample: a sample is considered negative if ADAs are not detected (ie, negative in screening assay or reactive in screening but negative in confirmatory assay).
- ADA-positive sample: sample in which ADA is detected, ie, sample generates an assay signal equal to or greater than the cut-point in the screening assay and is tested positive in the confirmatory assay.
- The ADA titer of the positive samples will also be assessed. A titer represents a quasi-quantitative information on the level of ADA present in a sample. Confirmed positive samples are serially diluted until a negative result is achieved. The titer is subsequently defined as the reciprocal of the last dilution that tests positive. The minimal required dilution (MRD) will be incorporated in the final calculation.
- The ADA attributes will be determined by the following conditions (note that some cases may not be applicable to the current study due to the treatment naïve study population):
- Pre-existing ADAs: antibodies reactive with the study drug present in subjects before treatment. The week 49 timepoint will provide data on pre-existing ADAs to avalglucosidase alfa in the alglucosidase alfa treatment arm.
- Treatment induced ADAs: ADAs developed de novo (seroconversion) following administration of the study drug. If the baseline ADA sample is missing or non-reportable and at least one reportable on-treatment ADA sample is available, the baseline sample will be considered as “negative”.

- Treatment boosted ADAs: Pre-existing ADAs that were boosted at least two titer steps from baseline (ie, 4 fold increase in titers) following administration of the study drug (any time after the first drug administration).

The following kinetics of the ADAs will be analyzed:

- Onset of ADA is defined as the time period (in days) between the first study drug administration and the first instance of treatment induced ADAs.
- Duration of ADA will be calculated as the date of last treatment induced ADA sample minus date of first treatment induced ADA sample + 1.

The following ADA response classifications will be used:

1. Treatment-induced ADA- patients are ADA negative at baseline and have developed an ADA response
 - a. Transient ADA response is defined as: 1) Treatment-induced ADA detected only at one sampling timepoint post-baseline (excluding the last sampling time point); or 2) Treatment-induced ADA detected at two or more sampling time points post-baseline, where the first and the last ADA-positive samples (irrespective of any negative samples in between) are separated by a period of less than 16 weeks, and the subject's last sampling time point is ADA-negative
 - b. Persistent ADA response is defined as: 1) Treatment-induced ADA detected at two or more sampling time points post-baseline, where the first and the last ADA-positive on-treatment sample (irrespective of any negative samples in between) are separated by at least 16 weeks; or 2) Treatment-induced ADA detected in the last two sampling time points, irrespective of the time period in between.

The following subclassifications for persistent ADA response will be considered as well. The titer values are based on LOTS alglucosidase alfa clinical experience.

- Low response – if a patient peak titer ≤ 800 and positive at final assessment. This represents the first titer that is greater than a 4-fold increase from the assay minimum required dilution (MRD). Titers within this range would be considered as Low response.
 - Intermediate response – if a patient was persistently seropositive but titer is 1600-6400 and is positive at final assessment.
 - High response – if a patient was persistently seropositive and titer is ≥ 12800 and is positive at final assessment.
 - Tolerized – if a patient was persistently seropositive, but negative at the final assessment.
- c. Indeterminate ADA response – if the patient developed ADA at the last time point and all previous samples are ADA negative, therefore cannot determine whether the response will be transient or persistent in duration.

2. Treatment-boosted ADA – patients have pre-existing ADA (positive at baseline or study entry) and have ADA titers boosted to a higher level by a greater than or equal to four-fold increase (i.e., by greater than at least twice the dilution level).
3. Treatment emergent ADA- combination of treatment induced and treatment boosted

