2.6.8.2 Duration of ADA

The kinetics and duration of the immune responses will be analyzed as follow:

- Onset time of ADA will be analyzed descriptively using summary statistics minimum, Q1, median, Q3 and maximum.
- Duration of ADA will be analyzed descriptively using summary statistics minimum, Q1, median, Q3 and maximum. It will only be calculated for the patients with at least two ADA positive samples. The median duration and the quartiles will be reported.

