2.6.8.5 Neutralizing ADA

- Incidence of neutralizing antibodies (inhibition of enzyme activity and inhibition of enzyme uptake) will be reported for both treatment naïve and switch patients
- Onset time of neutralizing ADA will be analyzed descriptively using summary statistics minimum, Q1, median, Q3 and maximum.
- Duration of neutralizing ADA will be analyzed descriptively using summary statistics minimum, Q1, median, Q3 and maximum. It will only be calculated for the patients with at least two neutralizing ADA positive samples.

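### ADA duration pools ended and ongoing responses without censoring, so the data cut caps its upper quantiles, and its median too if about half or more of the patients are still positive

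*SAP*

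**What the plan says.** SAP 2.1.4.8 (Immunogenicity) gives the formula: "Duration of ADA will be calculated as the date of last treatment induced ADA sample minus date of first treatment induced ADA sample + 1". I read the two samples as the first and last positive ones.

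SAP 2.6.8.2 (Duration of ADA) gives the summary: "Duration of ADA will be analyzed descriptively using summary statistics minimum, Q1, median, Q3 and maximum". It sets the inclusion rule, "It will only be calculated for the patients with at least two ADA positive samples", and adds: "The median duration and the quartiles will be reported".

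SAP 2.6.8.5 (Neutralizing ADA) has a parallel summary, "Duration of neutralizing ADA will be analyzed descriptively using summary statistics minimum, Q1, median, Q3 and maximum", with its own inclusion rule, "It will only be calculated for the patients with at least two neutralizing ADA positive samples". It gives no duration formula.

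None of these sections defines an end of response, a censoring rule or a Kaplan-Meier estimate, or separates cleared patients from those still positive. The protocol's immunogenicity analysis (11.4.4.4) covers seroconversion, time to seroconversion and titers, and has no duration method that would fill the gap.

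The SAP does expect patients to be positive at the end. The high persistent class in 2.1.4.8 applies "if a patient was persistently seropositive and titer is ≥ 12800 and is positive at final assessment"; the low and intermediate classes also require a positive final assessment. Only the tolerized class of persistent responders ends negative.

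**The concern.** For a patient who is positive at the last sample, the response has not been seen to end. Its duration is right-censored, yet the formula enters the last sample date as if it were the end. Quartiles and a median over a mix of completed and unfinished times partly describe how long patients were observed after turning positive, not how long antibodies last.

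What is at stake is the reading of one immunogenicity table. If many patients stay positive, very different antibody processes can yield the same reported median, and the same process can yield very different medians at the Week 49 lock and at a later extension cut. The SAP handles the same problem properly elsewhere: 2.5.3.4.2 plans Kaplan-Meier summaries for changes in respiratory support and censors patients without an event.

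**Working it through.** The documents give no figure for ADA duration, so there is none to reproduce. The check has two parts.

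**1. Value for a patient still positive at the cut**

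Inputs: the formula in SAP 2.1.4.8, and nominal days as 7 × (week − 1) + 1. This matches the Week 49 (Day 337) and Week 145 (Day 1009) targets in SAP Table 14, which is the efficacy window table.

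Value = cut-off day − first positive day + 1.

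| First positive | Cut at Week 49 | Cut at Week 145 |
|---|---|---|
| Week 5 (Day 29) | 337 − 29 + 1 = 309 | 1009 − 29 + 1 = 981 |
| Week 9 (Day 57) | 337 − 57 + 1 = 281 | 1009 − 57 + 1 = 953 |
| Week 13 (Day 85) | 337 − 85 + 1 = 253 | 1009 − 85 + 1 = 925 |

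True duration does not enter. These are nominal values; the ±7-day visit window for safety assessments moves them slightly.

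**2. When the pooled quantiles are affected**

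Closed form, assuming every patient turns positive at Week 9 and durations are exponential with median M days: the share still positive at Week 49 is 2^(−281/M).

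- M = 365: 2^(−281/365) = 59%
- M = 730: 2^(−281/730) = 77%
- M = 1460: 2^(−281/1460) = 88%

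All three exceed half, so the reported median is 281 days each time. That follows from choosing true medians longer than the window, so shorter ones need checking too.

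That was done by simulation: 20,000 patients per scenario on the SAP sampling schedule (Week 2, then "every month during the blinded treatment period and for the first 6 months of the open-label avalglucosidase alfa long term follow-up phase", then every 3 months), with the two-positive rule applied. Assumptions not in the documents: first positive at Week 5, 9 or 13 with probability 0.4, 0.4 and 0.2; exponential clearance with the stated mean; in the last row, 90% never clear. Kaplan-Meier (KM) is run on the same patients, censoring those positive at their last sample.

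| Scenario (true median) | Cut | Still positive | SAP Q1 / median / Q3 | KM median |
|---|---|---|---|---|
| Mean 200 d (139 d) | Week 49 | 28% | 85 / 141 / 253 | 141 |
| | Week 145 | 1% | 85 / 141 / 281 | 141 |
| Mean 400 d (277 d) | Week 49 | 53% | 141 / 253 / 281 | not reached |
| | Week 145 | 10% | 141 / 281 / 533 | 281 |
| Mean 800 d (555 d) | Week 49 | 72% | 253 / 281 / 309 | not reached |
| | Week 145 | 31% | 253 / 561 / 925 | 561 |
| 90% never clear (none) | Week 49 | 94% | 281 / 281 / 309 | not reached |
| | Week 145 | 91% | 925 / 953 / 981 | not reached |

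At 28% still positive the median is right, and only the upper quartile is held down (253 days, against 281 when almost all responses have ended). From 53% upward the Week 49 median sits at one of the ceilings in part 1. In the last scenario, moving the cut from Week 49 to Week 145 takes the reported median from 281 to 953 days with no change in the antibody process.

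**The case against.** The best defence is that the SAP defines an observed interval, first to last positive sample, and computes it consistently. It does not claim to estimate time to clearance. SAP 2.6.8.4 reports numbers and percentages for transient, persistent (with subclasses) and indeterminate responses, so a reader can largely recover how many responses were unresolved; 2.6.8.3 adds last titers and titer plots. Safety analyses are essentially descriptive with no inferential testing (2.6), and 1.6 says some immunogenicity revisions follow an integrated plan that we do not have. Kaplan-Meier also needs an event, and the SAP defines none for loss of positivity; its response classes ignore negatives that fall between positives.

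Much of this stands. The response counts limit misreading, and the event rule has to be written. But counts in another table do not correct a pooled median, and the duration sections do not label it as observed to date.

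On comparisons between arms, the objection is largely right for the blinded period: both arms share one planned cut, so the harm there is a ceiling that hides differences rather than one that creates them. In the extension, follow-up does vary. Switch patients start avalglucosidase alfa at Week 51 (Day 351), 350 days after Day 1, and the extended phase can end at country approval.

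**Conclusion.** The rule as stated gives upper quantiles capped by the data cut, and a capped median once about half or more of the included patients are still positive. This is a minor point about a descriptive immunogenicity summary, with no bearing on the primary test or alpha.

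Three stronger readings are tempting and not supported:

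- A reader might infer that the reported median is simply the length of follow-up. The SAP reports one median over everyone with at least two positive samples. It reaches the ceiling only if enough of them are still positive, and the documents do not give that share. The ceiling itself runs from the first positive sample, not from the first infusion.
- A reader might infer that the median is always biased low. At 28% still positive it is not, and the two-positive rule drops the shortest responses, which pushes the median up.
- A reader might infer that neutralizing ADA is computed by the same formula. SAP 2.6.8.5 gives matching summary statistics but no formula, so that part is a gap to fill.

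The ceilings in days follow from the SAP formula and nominal visit days. The simulated medians rest on assumed onset and clearance and only illustrate the range.

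**What to change.** Revise SAP 2.1.4.8, 2.6.8.2 and 2.6.8.5 as follows.

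- Estimate duration by Kaplan-Meier from the first positive sample.
- Count the response as ended, at the last positive sample, only if the patient's last reportable sample is negative. Among patients with at least two positive samples these are the SAP's transient and tolerized patients. Ignore intermittent negatives, as the response classes already do.
- Censor patients positive at their last reportable sample at that sample.
- Report the median, or that it was not reached, with the number still positive, the analysis period and the cut-off used.
- State whether the two-positive inclusion rule is kept.
- Write the formula and the same rule for neutralizing ADA.

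Cost: SAP wording and programming only, with data already collected and a method the SAP already uses. The median may be not reached. An ended response is dated to its last positive sample, so it can be understated by up to one sampling interval (monthly, later 3-monthly), and ended status holds only as of the cut-off. If Kaplan-Meier is not wanted, the minimum is to report cleared and still-positive patients separately and label the latter as observed to date.

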2.1.5 Infusion associated reactions (IARs)

Protocol-defined IARs

IARs are defined as AESIs that occur during either the infusion or the observation period following the infusion which are deemed to be related or possibly related to the IMP. At the discretion of the Investigator, AEs occurring after completion of the post-infusion observation period that are assessed as related may also be considered infusion associated reactions (IAR).

Algorithm-defined IARs

An alternative definition of IAR is defined as any treatment-emergent AE meeting one of the following criteria:

- a) Event occurs from the start of infusion to the end of infusion plus 24 hours window, and considered related to study drug, ,
- b) If AE start date is non-missing but time component is missing, compare AE Start date with infusion start date (date component only) and infusion end date (date component only). If AE Start date is between infusion start date and infusion end date plus 1 day, consider such AE as Algorithm -defined IAR if AE is related to study drug (missing relatedness is assumed related).

2.1.6 Pharmacokinetic endpoints

Pharmacokinetic variables include C_{max} , AUC_{0-last} , total body clearance of a drug from the plasma and volume of distribution, if appropriate.

2.1.7 Pharmacogenetic endpoints

Pharmacogenetic endpoints include mutations within the GAA gene and ACE allele genotype status. The genetic results obtained from this study are not diagnostic and will be used for research purposes only.

2.1.8 Pharmacodynamic endpoints

Pharmacodynamic endpoints include the urinary Hex4 level.

2.1.9 Patient Global Impression of Change

The PGIC items will be completed at Week 49 (the conclusion of the PAP), and will be administered annually in follow-up during the extension period. The PGIC items consist of

4 questions pertaining to overall disease-related symptoms, activities of daily living, as well as mobility and respiratory issues. The items range from -3 (a great deal worse) to 0 (no change) to 3 (a great deal better). The data from this scale will be used to support and validate additional endpoints in the trial.

2.1.10 Quality of life/health economic variables/other endpoints

The following endpoints are included:

- The PDSS and PDIS will be completed via an e diary daily for 2 weeks between visits according to the protocol specified schedules. Patients ≥ 18 years of age at screening/baseline will complete this assessment through both a 24-hour recall version administered daily during the screening period, as well as a 7-day recall version administered prior to the first infusion. The PDSS and PDIS are both self-administered questionnaires specifically designed to capture the symptoms and impacts pertinent to patients with LOPD. The PDSS contains 12 questions on a scale from 0 (none) to 10 (as bad as I can imagine), while the PDIS contains 15 questions with varying scales implemented depending on question type.
- The R-PAct scale will be completed in selected countries (ie, UK, USA, Canada, Belgium and The Netherlands). Patients whose first language is English or Dutch and who are ≥ 18 years of age at screening/baseline will complete this assessment. During the treatment period, the assessment will be completed before IMP infusion if possible. The R-PAct is a self-administered questionnaire specifically suited to quantify the effects of Pompe disease on patient's ability to carry out daily activities and their social participation. It consists of 18 items suited to quantify activity limitations, ranging from unable to perform daily life activities (0) to able to perform without difficulty (2) in patients with Pompe disease (26).

These endpoints are exploratory endpoints that are specific to Pompe disease. The PDSS/PDIS are scales recently developed within Sanofi, and the scoring method will be developed following the completion of an external validation study. These will be described and documented in a separate analysis plan.

